sensitive and specific to progression or improvement in clinical status of the patient. We will therefore correlate scores on the Comorbidity Index, Kubo INPH Scale, Kiefer's index domains for gait/balance, headache and dizziness, European NPH Scale, INPH Diagnosis Checklist with the Black Outcome Scale, Marmarou Recovery Scale, modified Rankin scale, Barthel index. Furthermore, we would test the hypothesis of association of NPH with congenital hydrocephalus or early childhood changes in brain (long standing overt ventriculomegaly) which may manifest as large heads. We will correlate head circumference at baseline and with outcomes at various time points.

4. Study Procedures

[figure not shown]
a. Study design, including the sequence and timing of study procedures (Distinguish research procedures from those that are part of routine care).

Page 4 of 11

Principal Investigator: [name]

Application Number: NA_00042178

Follow-up at 6, 12, 18, 24 months for long-term response rates

The study is a randomized 2x2 double-blinded cross-over design study with two armscomparing optimally functioning shunts (Optimal drainage) to the placebo treatment wherein there is minimal CSF flow through the shunts (sub-optimal drainage). The state of sub-optimal drainage of shunt will be attained by raising the opening pressure of the shunt valve to maximum which will impede the CSF flow. All patients who are candidates for shunt surgery based upon standard of care practice of CSF drainage trial will enter the study. Only patients who are not at significant risk of falls will be included in the study i.e patients with Tinetti score >18. Furthermore, the neurosurgeon/neurologist will not be blinded to patients shunt valve status. Only the nurse practioner or physiotherapist performing the study evaluation would be blinded. All evaluation data would be made available to neurologist/ neurosurgeon remain informed about treatment failure (Tinetti Gait and evaluation <18).

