During the initial phase of the study, participants will be randomized in 1:1 allocation ratio to optimally and sub-optimally draining shunt arms. After completion of six weeks the opening pressures for patients in the optimally draining shunt arm will be raised to minimize CSF flow (crossover to sub-optimally draining arm). Likewise, at 6 weeks patients initially in suboptimal drainage arm will have the opening pressures appropriately reduced so that flow through the shunt is optimal (crossover to optimal drainage shunt arm). X-rays will be performed to confirm shunt valve settings. Since the shunt is only effective during the time it is effectively draining and the carryover effect is minimal (i.e., often lasting for no more than a few days), there will be no washout period between arms. Patients will undergo every third week evaluations regardless of the study arm to evaluate safety as well as efficacy. Patients and the psychometrician, physical therapist and nurse practitioner who assess the outcome measures will be blinded to the shunt status. Only the study neurosurgeon and neurologist will be aware of the shunt status, and will make clinical (safety) decisions after being informed of Tinetti gait and balance scores. The follow-up and evaluation timeline is indicated in the algorithm above. The Neurosurgeon will be notified about the gait and balances score and will make a clinical (safety) decision accordingly. Any patient whose gait deteriorates to Tinetti < 18 or has a fall will be regarded as a treatment failure. Patients who are a treatment failure during the

Principal Investigator: [name]

Application Number: NA 00042178

suboptimal drainage arm will have the opening pressure of the valve adjusted. These patients would then be considered to be crossed over to draining arm if they were in the initial suboptimal drainage arm of the study. If a patient who has already been crossed over from optimally draining shunt to sub-optimally draining shunt arm worsens, s/he will have the shunt pressure turned down and will be followed according to standard of care protocol at 6 monthly intervals. During this time, we will collect data on these follow-up visits as part of the research.

Standard of care procedures: Shunt surgery, Post op evaluations while shunt is in optimal drainage setting, 6, 12 months, 18 months and 24 months post-op visit

Research procedures: Visits during non-draining shunt period

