b. Study duration and number of study visits required of research participants.

The study duration and number of visits for each participant will vary depending on the arm of the study the patient enters first (flow chart above).

Non-Draining → Draining Shunt arm

Baseline preoperative visit → Shunt surgery → Sub-optimally draining shunt → first visit within 2 weeks from surgery 6 weeks visit, → cross over to draining Shunt arm at 6 week visit along with x-rays confirmation of the new valve settings → 9 weeks visit → 12 weeks visit Total duration 12 weeks from shunt surgery

Number of total Visits=4

Draining → Non-Draining Shunt arm

Baseline preoperative visit → Shunt surgery → Draining shunt → first visit within 2 weeks from first surgery →, 6 weeks visit, → cross over to non-draining Shunt arm at 6 week visit along with x-rays confirmation of the new valve settings → 9 weeks visit → 12 weeks visit Total duration 12 weeks from shunt surgery

Number of total Visits=4

- c. Blinding, including justification for blinding or not blinding the trial, if applicable.

 Patients and raters will be blinded to treatment status to minimize reporting bias. Neurologist and neurosurgeons will not be blinded for safety reasons.
- d. Justification of why participants will not receive routine care or will have current therapy stopped.

The study is designed to compare efficacy of shunt in comparison to sham/placebo (non draining shunt). Though shunt is standard of care it has not been systematically evaluated in a randomized trial. The length of time that a patient will have a non-draining shunt has been limited to 6 weeks and will be shortened if the patient shows a worsening in gait while on that arm.

e. Justification for inclusion of a placebo or non-treatment group.

The placebo arm is included to take into account any placebo effect. Current standard of care treatment of normal pressure hydrocephalus has not been evaluated in a placebo controlled trial. Current guidelines are based on studies which lack a comparison with placebo and their

Principal Investigator: [name]

Application Number: NA 00042178

outcomes have been highly variable. Thus a placebo control is needed to evaluate efficacy of shunt and to improve our selection criteria for shunt insertion.

f. Definition of treatment failure or participant removal criteria.

Failure: Any participant whose gait deteriorates to Tinetti≤18 will be considered a

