treatment failure as this is considered under standard of care to be high risk of fall.
Additionally any patient falling due to inability to balance or poor gait would also be
considered a treatment failure.

Any patient deteriorating to failure level or having a fall attributable to gait impairment will be recorded as a treatment failure for that arm of the study and if on suboptimal drainage arm will be crossed over to optimal drainage level.

Patients who fail would however continue to participate in study and data will be collected at all subsequent follow-up points regardless of the study arm as described above. Furthermore, for concerns of patient safety no patient who fails (Tinetti \leq 18) will subsequently have suboptimal drainage in shunt at anytime^{12,13}.

Response:

Gait

- Tinetti gait and balance scale: Measured with respect to baseline (pre-drainage trial scores)
- 2. TUG: Measured with respect to baseline (pre-drainage trial scores)
- 3. MCV Gait Grade: Measured with respect to baseline (pre-drainage trial scores)

Cognition

- 1. Mini Mental State Examination (MMSE)
- 2. Rey Auditory Verbal Learning Test (RAVLT): Measured with respect to baseline (pre-drainage trial scores)
- 3. Trail Making Test A & B: Measured with respect to baseline (pre-drainage trial scores)
- 4. Writing the Alphabet: Measured with respect to baseline (pre-drainage trial scores)
- 5. Beck Depression Inventory

Principal Investigator: [name]

Application Number: NA 00042178

- 6. Stroop test
- 7. Pegboard

Urinary

- 1. Urinary Incontinence Questionnaire (ICIq-UI): Measured with respect to baseline (predrainage trial scores)
- 2. Overactive Bladder Questionnaire (ICIq-OAB): Measured with respect to baseline (predrainage trial scores)
- 3. Quality-of-Life related to lower urinary tract symptoms (**ICIq-LUTSqol**): Measured with respect to baseline (pre-drainage trial scores)
- 4. Global quality-of-life assessment (**AUASSqol**): Measured with respect to baseline (predrainage trial scores)
- 5. Voiding Diary

Functional Scales

- 1. Barthel Index: measured with respect to baseline (pre-drainage trial scores)
- 2. Modified Rankin Scale
- g. Description of what happens to participants receiving therapy when study ends or if a participant's participation in the study ends prematurely.
- Inclusion/Exclusion Criteria3.1 Inclusion Criteria

 - Age of Patients (between 55 to 85 years old)
 - Clinically suspected iNPH with at least gait impairment.

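### Sections 4a and 4f define treatment failure differently (Tinetti below 18 or any fall, against 18 or below or a gait- or balance-related fall), and no text says which governs

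*Combined protocol and SAP*

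**What the plan says.** Section 4a (study design) gives the failure threshold twice. Where it explains what the unblinded clinicians are told, they are to "remain informed about treatment failure (Tinetti Gait and evaluation <18". Where it sets out the crossover, it adds falls without any condition on cause: "Any patient whose gait deteriorates to Tinetti < 18 or has a fall will be regarded as a treatment failure".

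Section 4f, which is headed as the definition of treatment failure, puts the boundary on the other side of 18: "Any participant whose gait deteriorates to Tinetti≤18 will be considered a" treatment failure, on the ground that this level is a high fall risk under standard of care. Its fall rule is conditional on cause: "Additionally any patient falling due to inability to balance or poor gait would also be" a failure. It then says that a patient "having a fall attributable to gait impairment will be recorded as a treatment failure for that arm of the study". Section 4f also bars any later sub-optimal drainage for a patient who fails, and states the 18-or-below threshold again in that sentence.

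Two other rules allow rescue without a numerical cut-off. In section 4a, a patient already crossed over to sub-optimal drainage who "worsens, s/he will have the shunt pressure turned down and will be followed according to standard of care protocol at 6 monthly intervals". In section 4d, time with a non-draining shunt "will be shortened if the patient shows a worsening in gait while on that arm".

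Section 7c does not define failure. For a patient who is a treatment failure and is taken off an arm, it carries the measurement at failure forward as the six-week value. Entry requires a Tinetti score above 18 (3.1 Inclusion Criteria).

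**The concern.** Failure status is not merely descriptive in this trial. It determines what is recorded against an arm, it prompts the valve change in the non-draining period, and it is a condition of the carry-forward rule in the primary analysis. A status with those consequences needs one definition. Here there are two, they differ in both the score and the fall component, and neither section refers to the other.

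The fall component has a further difficulty. Section 4f requires someone to attribute the fall to gait or balance but does not say who. Under section 4a the neurosurgeon and neurologist, who make the safety decisions, know the valve setting. If the rule is settled case by case during the trial, the attribution may be made by someone who knows the treatment. That is a risk, not a demonstrated bias.

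**Working it through.** **Step 1. Set the two definitions side by side.**

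| Patient | Section 4a | Section 4f |
|---|---|---|
| Score 17 or lower | failure | failure |
| Score exactly 18, no fall | not named as failure | failure |
| Score above 18, fall from poor gait or balance | failure | failure |
| Score above 18, fall from another cause | failure | not named as failure |
| Score above 18, no fall | not failure | not failure |

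The texts diverge in the second and fourth rows only. A patient scoring 18 who also falls fails under both.

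**Step 2. Trace the consequences in the non-draining period.**

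- Failure record: changes for every patient in those two rows.
- Valve change triggered by failure: depends on the section used. For a patient scoring 18, the rules on worsening in sections 4a and 4d offer another route to the same action, because everyone entered above 18.
- Carry-forward: matters only before the end of a period, for example at the first visit after surgery (non-draining first) or at week 9 (draining first). At week 6 or week 12 the value at failure is already the end-of-period value. In the draining period carry-forward has little role, because the prescribed valve change applies to the sub-optimal arm.

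**Step 3. Reproduce the plan's sample size, used below as the denominator.** Inputs from section 7c: difference 5, SD 5, two-sided alpha 0.05, power 80%, total 34, dropout 20%, 42 after adjustment. A two-group t-test with 17 per group has power 80.7% (16 per group gives 78.1%), so 34 reproduces. 34/0.8 = 42.5, against the stated 42. Neither figure is in dispute here.

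**Step 4. Weight of one reclassified patient.** With equal sequences of N/2 patients, the period-adjusted treatment estimate is half the difference between the two sequences' mean period differences. Changing one patient's period value by k moves that sequence's mean by k/(N/2), and the estimate by half of this, k/N.

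| k (assumed) | N = 34 | N = 42 |
|---|---|---|
| 1 | 1/34 = 0.029 | 1/42 = 0.024 |
| 2 | 2/34 = 0.059 | 2/42 = 0.048 |
| 5 | 5/34 = 0.147 | 5/42 = 0.119 |

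As a share of the 5-point target, k = 5 is 0.147/5 = 2.9% or 0.119/5 = 2.4%. Three such patients, all shifted the same way, give 3 × 0.147 = 0.44 or 3 × 0.119 = 0.36 points.

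Against sampling error at N = 34: if the SD of 5 is that of the within-patient difference, the standard error is 5/√34 = 0.86 and one patient at k = 5 moves the estimate by 0.147/0.86 = 0.17 standard errors. On the two-group reading that reproduces 34, it is 5 × √(2/17) = 1.71, and the shift is 0.147/1.71 = 0.09.

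The documents do not give k or the number of patients affected.

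**The case against.** The best reply is that the sections can be read together. Each states a sufficient condition and neither says only, so failure would be a score of 18 or below or any fall. Alternatively, section 4f governs because its heading says it is the definition. Both readings are reasonable, and both make a score of 18 a failure. But they disagree about a fall unrelated to gait or balance, which fails under the first and not under the second. The first also leaves section 4f's condition on cause with nothing to do. Either is an inference that the text does not state.

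It may also be said that the threshold difference is loose notation or a symbol lost in reading the file. The entry and exclusion lists leave the boundary value unassigned for MMSE, Tinetti and Kiefer alike, so this is possible. It would not remove the finding, because the fall rules differ in words.

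The objection that the practical effect is narrow stands. If section 4d is followed, a patient scoring 18 may be turned down anyway. There is then no full-period non-draining score to compare with, so the k/N figures are illustrations only.

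A reader might infer three larger problems, which the documents do not support.

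- **A safety gap.** The rules on worsening, and the reporting of scores to the neurosurgeon, give other written routes to rescue.
- **A conflict over crossing a draining-first patient with a score of 18.** The week-6 instruction, "After completion of six weeks the opening pressures for patients in the optimally draining shunt arm will be raised to minimize CSF flow", states no exception. But the ban in section 4f is specific, carries its own threshold of 18 or below, and is naturally read as the exception.
- **Missing primary values caused by the discrepancy.** A draining-first patient scoring 17 fails under both sections, meets the same ban and leaves the same absent sub-optimal value. The absence of a section 7c rule for a patient turned down for worsening without being a failure is likewise a separate gap. Neither is part of this point.

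**Conclusion.** The point holds. The protocol contains two incompatible definitions of treatment failure and gives neither precedence. It should be fixed, because failure status drives actions and an analysis rule, and because the remedy costs almost nothing. It is a rule that is wrong as written, not a missing detail.

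The size is modest. The difference reaches only patients with a score of exactly 18 and no fall, and patients above 18 with a fall from another cause. Each changes the failure record. Each can change the primary estimate only through a value before the end of the non-draining period, by k/N: at most 0.15 points for the k values shown. The documents do not support a claim of material bias in the primary result.

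This rests on an assumed k, on equal sequence sizes, and on the written text. The flow diagram cited in section 4a is not shown, so whether it states a failure rule could not be checked.

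**What to change.** 1. In both places in section 4a, change the threshold from below 18 to 18 or below. This matches the level that section 4f calls high fall risk and is the complement of the entry criterion.
2. Use one fall rule in sections 4a and 4f. Any fall is preferable: it satisfies both texts and needs no attribution of cause by clinicians who know the valve setting.
3. In section 7c, have the carry-forward rule refer to that single definition.

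The cost is a wording amendment, with no added patients, visits or measurements. The one downside of the any-fall rule is that some falls unrelated to gait will count as failures.

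### Section 4f's bar on later suboptimal drainage names only the Tinetti score, so a draining-first patient who fails by a fall is not expressly protected from the week-6 valve raise

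*Combined protocol and SAP*

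**What the plan says.** Section 4f (treatment failure and removal) sets out two routes to failure. The first is deterioration to a Tinetti score of 18 or less. The second is a fall: "Additionally any patient falling due to inability to balance or poor gait would also be" counted as a failure. A failure by either route is recorded against the current arm, and the patient "if on suboptimal drainage arm will be crossed over to optimal drainage level". Failure does not end participation: "Patients who fail would however continue to participate in study".

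The safety bar follows. It opens "Furthermore, for concerns of patient safety no patient who fails (Tinetti", completes the parenthesis with the ≤18 threshold, and says that no such patient "will subsequently have suboptimal drainage in shunt at anytime".

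Section 4a (study design) sets the crossover for the draining-first order: "After completion of six weeks the opening pressures for patients in the optimally draining shunt arm will be raised to minimize CSF flow". Section 4b repeats this crossover at the week-6 visit and then lists visits at weeks 9 and 12. Neither section states an exception for patients who have already failed. Section 4a also says that the unblinded neurosurgeon and neurologist "will make clinical (safety) decisions after being informed of Tinetti gait and balance scores", and it refers to a diagram for the schedule: "The follow-up and evaluation timeline is indicated in the algorithm above". That diagram is not reproduced in the text available.

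**The concern.** The bar is there to keep a patient who has failed from being put back on minimal drainage. Section 4f explains the Tinetti threshold as a marker of high fall risk. As worded, the bar expressly covers patients who reach that marker but not those who have had the fall itself. Every participant must enter with a score above 18, so a gait-related fall while still above the threshold is possible.

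If site staff took the parenthesis as the full scope of the bar, a patient already recorded as a treatment failure could have the valve set to maximum opening pressure at week 6. Whether a safety rule reaches such a patient should not depend on how a parenthesis is read.

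**Working it through.** The question is textual, so the check is to take each way a patient can fail and see which stated rule governs the valve afterwards.

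| Order and period of failure | Route | What the visible text says about the valve |
|---|---|---|
| Suboptimal first, period 1 | Either | Moved to drainage at once (4a, 4f); no later suboptimal period is scheduled |
| Suboptimal first, period 2 (draining) | Either | Already draining; no later suboptimal period is scheduled |
| Draining first, period 2 (suboptimal) | Either | Pressure turned down, then follow-up every 6 months (4a, 4f) |
| Draining first, period 1 | Tinetti ≤18 | Bar in 4f expressly stops the week-6 raise |
| Draining first, period 1 | Gait-related fall, Tinetti >18 | No express rule: the valve change on failure applies only to the suboptimal arm, the bar's parenthesis does not name falls, and the week-6 raise is unqualified |

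Only the last row is open. Two other places in 4a lean towards the score alone. One equates treatment failure with a Tinetti score below 18. The other ties the clinicians' safety decisions to the Tinetti scores. (The difference between below 18 in 4a and 18 or less in 4f is a separate matter.)

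**The plan's own sample size.** The finding does not depend on it, but the total of 34 reproduces. A two-sided two-sample t-test at 0.05 with a difference of 5 and an SD of 5 has power 0.781 with 16 per group and 0.807 with 17 per group, and 2 × 17 = 34. Allowing for 20% dropout, 34/0.8 = 42.5; section 7c states 42.

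**Ceiling on the affected group.** With 1:1 allocation, 42/2 = 21 patients are draining-first. One affected patient is 1/21 = 4.8% of that order and 1/42 = 2.4% of the planned sample.

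**Exposure per affected patient, if the narrow reading were applied.** From the raise to the next scheduled visit: week 9 − week 6 = 3 weeks. To the end of the period: week 12 − week 6 = 6 weeks at most.

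**Dropout allowance.** 42 − 34 = 8 patients.

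**The case against.** The strongest reply is that the bar already covers these patients. Its operative words refer to a patient who fails; 4f has just defined failure by both routes; and the sentence immediately before the bar uses the same verb for both. On that reading the parenthesis is shorthand. This is probably what was intended, and nothing here shows that such a patient must be raised.

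The silence of 4a and 4b is also weak evidence. They make no exception for Tinetti failures either, although 4f plainly exempts those patients, so they read as default sequences that 4f overrides. The flow chart could carry an exception.

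There are real safeguards besides. Section 4c leaves the neurologist and neurosurgeon unblinded for safety without limiting them to Tinetti scores, and 4a gives them all evaluation data. Section 4d shortens the suboptimal period if gait worsens, and a further gait-related fall would itself return the patient to drainage. For harm to follow, an unblinded clinician would have to raise the valve in someone already recorded as a failure.

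All of this stands, and it limits the seriousness of the point. It does not remove the mismatch. The sentence that prohibits re-exposure names one of the two routes that the same section defines, and the score-only shorthand in 4a makes the narrow reading plausible. If protection is intended, writing it down changes nothing the sponsor wants.

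**Conclusion.** The point holds in a limited form. The written scope of the bar is narrower than the protocol's own definition of failure, and a draining-first patient who fails by a gait-related fall with a Tinetti score above 18 has no express protection from the week-6 raise. It is a low-severity safety ambiguity, worth a cheap correction; it does not alter the analysis method or the sample size calculation.

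The 21 is the size of the draining-first order, not a forecast. The true number depends on the rate of gait-related falls during drainage, which the documents do not give, and it could be zero. The exposure figures assume that the narrow reading is applied and that no earlier worsening or fall brings the valve down. The conclusion also assumes that the flow chart contains no exception for failed patients.

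**What to change.** In the bar in section 4f, replace the parenthesis with: *(Tinetti ≤18 or a fall attributable to gait or balance)*. This follows 4f's own two-route definition. Because the sentence already applies without limit of time, the amended bar overrides the week-6 raise and the visit schedule, and no other edit is strictly needed. A matching cross-reference beside the week-6 raise in 4a would be a harmless addition.

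The drafting cost is one phrase. The statistical cost is that any patient so protected would have no suboptimal-period value, as already happens for draining-first patients who fail on the Tinetti score. The carry-forward rule in section 7c does not supply one, because it fills in the arm in which the patient failed. If such patients are left out of the paired comparison, each uses one of the 8 places allowed for dropout.
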